2. DESIGN AND METHOD

2.1 Study Site:

Study will be conducted University of Peradeniya.

2.2 Study Population:

Undergraduates who are currently having upper back pain for more than seven days will be selected as sample. Participants who will have sub-acute and chronic pain which means who will have pain more than a week or seven days will be selected as sample and who have subjected to any recent surgeries, recent fractures, accidents or injuries in upper back will be excluded from the study.

2.3 Study Setting:

Study will be conducted in Service unit of Department of physiotherapy at University of Peradeniya.

2.4 Study Design:

This study is a Randomized Control Trial, Double- Blinded study. Participants and assessors will be blinded. Participants will be allocated randomly in to two groups which are experimental group which will receive thoracic mobility exercises and control group which will receive myofascial release and joint mobilization treatment.

2.5 Hypothesis:

1. Hypothesis about difference in baseline characteristics of participants between control and experimental groups

Null Hypothesis: $H_0: \mu_1 - \mu_2 = 0$

There is no difference in baseline characteristics of participants between experimental and control group.

Alternate Hypothesis: $H_1: \mu_1 - \mu_2 \neq 0$

There is a difference in baseline characteristics of participants between experimental and control group

2. Hypothesis about differences in pain intensity between control group and experimental group.

Null Hypothesis: $H_0: \mu_1 - \mu_2 = 0$

There is no difference in pain intensity of participants between experimental and control group.

Alternate Hypothesis: $H_1: \mu_1 - \mu_2 \neq 0$

There is a difference in pain intensity of participants between experimental and control group

3. Hypothesis about differences in thoracic mobility (Range of Motion) between control group and experimental group.

Null Hypothesis: $H_0: \mu_1 - \mu_2 = 0$

There is no difference in thoracic mobility of participants between experimental and control group.

Alternate Hypothesis: $H_1: \mu_1 - \mu_2 \neq 0$

There is a difference in thoracic mobility of participants between experimental and control group

4. Hypothesis about differences in muscle strength of spinal extensors between control group and experimental group.

Null Hypothesis: $H_0: \mu_1 - \mu_2 = 0$

There is no difference muscle strength of spinal extensors of participants between experimental and control group.

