Alternate Hypothesis: $H_1: \mu_1 - \mu_2 \neq 0$

There is a difference in muscle strength of spinal extensors of participants between experimental and control group

5. Hypothesis about differences in disability of participants between control group and experimental group.

Null Hypothesis: $H_0: \mu_1 - \mu_2 = 0$

There is no difference in disability of participants between experimental and control group.

Alternate Hypothesis: $H1: \mu_1 - \mu_2 \neq 0$

There is a difference in disability of participants between experimental and control group.

2.6 Sample Size:

Sample size is Calculated by using G*power 3.1.9.4 software by assigning power 80% effective size 0.5, type I error = 0.05 and type II error = 0.2. Therefore calculated sample size was 42. Drop down rate of participants is assigned as 25 %. Therefore final sample size which obtained is 60 (Kang, 2021).

2.7 Sampling method:

Simple Random Sampling will be used as sampling technique as well as 30 Participants will be randomly allocated to each group. Participant will be allocated to the groups by using lottery method.

2.8 Data collection:

Undergraduates who are having upper back pain more than 7 days will be selected as sample and those who are having any contraindications, recent surgeries, fractures, accidents will be excluded from the students. Informed consent will be obtained from the participants. Participants will be allocated to one group by blindly select the number by lottery method. Thirty participants will be allocated randomly to each group. Allocation was concealed. Assessors will not be aware of intervention or control group and collect the demographic data, Pain assessment, Range of Motion and muscle strength at the baseline and after two weeks of intervention.

2.9 Data collection tool:

Measurement tool contains two sections such as pre-test and post-test questionnaire. In Pre-test questionnaire, there are six sections which includes personal details of the participants, pain related questions, Measurement of range of motion at base line, muscle strength at base line and pain-self-efficacy Questionnaire (PSEQ) at base line. In Post-test questionnaire, there are 4 sections which include, pain related questions

mainly pain intensity after two weeks, muscle strength after two weeks, Range of motion after two weeks and pain-self-efficacy Questionnaire (PSEQ).

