In the sixth section, The Pain Self-Efficacy Questionnaire (PSEQ) is a 10-item questionnaire developed to assess the confidence people with ongoing pain have in performing activities while in pain. The PSEQ has high internal consistency (0.92 Cronbach's alpha) and test-retest reliability is high of a 3-month period.

	0 "not at all confident"	1	2	3	4	5	6 "completely confident"
1. I can enjoy things, despite the pain.							
2. I can do most of the household chores (e.g. tidying-up, washing dishes, etc.), despite the pain.							
3. I can socialise with my friends or family members as often as I used to do, despite the pain.							

4. I can cope with my pain in most situations.						
5. I can do some form of work, despite the pain. ('work' includes housework, paid and unpaid work).						
6. I can still do many of the things I enjoy doing, such as hobbies or leisure activity, despite pain.						
7. I can cope with my pain without medication.						
8. I can still accomplish most of my goals in life, despite the pain.						
9. I can live a normal lifestyle, despite the pain.						
10. I can gradually become more active, despite the pain.						

Table 2

2.10 Ethical Considerations:

Ethical approval will be obtained from the Institutional Review Board of Bangladesh Health Professional Institute. Written informed consent will be obtained from all the subjects who are willing to participate in the study. Participation in this research is entirely voluntary basis and the participants have the right to withdraw from the study at any time.

2.11 Outcome measures:

Baseline outcome measures are demographic characteristics of participants such as age, gender, BMI, family size, bread winner of the family, monthly income and financial

support for study; Pain duration; Pain intensity at present moment, sitting, forward bending, standing, walking, sleeping, transferring and pain when performing day to day activities; Range of Motion of thoraco-lumbar flexion and extension; Muscle strength of thoracic spine extensors and overall scale of Pain-Self- efficacy Questionnaire. After two weeks same outcome measures will be obtained other than demographic characteristics and pain duration.

2.12 Data analysis:

Two sample t test will be used to compare the group at baseline to determine the sample characteristics in the both group will be statistically equal. To find out the significant variation in the group after the intervention again two sample t test will be used.

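### The stated sample size of 42 does not follow from 80% power and an effect size of 0.5 for the planned t test, and the effect that 60 participants can detect is not stated

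*Combined protocol and SAP*

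**What the plan says.** Section 2.6 names G*Power 3.1.9.4 as the software and gives the inputs and result as "by assigning power 80% effective size 0.5, type I error = 0.05 and type II error = 0.2. Therefore calculated sample size was 42". It continues: "Drop down rate of participants is assigned as 25 %. Therefore final sample size which obtained is 60". It does not name the test family, the number of tails, the metric of the 0.5, the outcome, or a standard deviation or difference of interest.

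The test has to be read from the other sections:

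- Section 2.4: "Participants will be allocated randomly in to two groups".
- Section 2.5: every alternative is non-directional (the difference in means is not zero). For pain it reads "There is a difference in pain intensity of participants between experimental and control group".
- Section 2.7: "30 Participants will be randomly allocated to each group". The 42 is therefore a total, because the figure inflated from it, 60, is split 30 + 30.
- Section 2.12: "To find out the significant variation in the group after the intervention again two sample t test will be used". This is the only test named for comparing outcomes between the groups.

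**The concern.** A reader of section 2.6 will take it that the between-group comparison has 80% power at an effect of 0.5 with 42 analysed. The planned test does not give that under either usual meaning of 0.5, and the two meanings err in opposite directions. As d, 42 is about a third of what is needed (42/128 = 0.33). As f, 42 is more than is needed, but the target is a full standard deviation, which the plan never says.

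The reader therefore cannot tell what difference the trial could detect, and cannot weigh a non-significant result. Such a result is realistic here, because both arms receive active treatment and section 3 expects significant pain relief from both. The plan already reads a t test as evidence of sameness at baseline: section 2.12 uses it to "compare the group at baseline to determine the sample characteristics in the both group will be statistically equal". That sentence concerns baseline only, but the same reasoning applied after treatment, backed by a claim of 80% power at 0.5, would mislead.

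**Working it through.** **Inputs.** Alpha 0.05 and power 80% (section 2.6: "type I error = 0.05 and type II error = 0.2"); effect size 0.5, metric not given (2.6); two groups (2.4), 1:1 (2.7); two-sided (2.5); two-sample t test (2.12).

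**Formula.** With group sizes n1 and n2, the t statistic has n1 + n2 − 2 degrees of freedom and noncentrality δ = d·√(n1·n2/(n1 + n2)). Two-sided power is P(|T| > t(0.975)) under the noncentral t distribution. For two equal groups d = 2f, so f = 0.5 is d = 1.0.

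**Step 1: try to reproduce 42.**

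| Reading of 0.5 | Tails | n per group | Power at n | Power at n − 1 | Total |
|---|---|---|---|---|---|
| d = 0.5 | 2 | 64 | 0.8015 | 0.7952 | 128 |
| d = 0.5 | 1 | 51 | 0.8059 | 0.7989 | 102 |
| f = 0.5 (d = 1.0) | 2 | 17 | 0.8070 | 0.7814 | 34 |
| f = 0.5 (d = 1.0) | 1 | 14 | 0.8241 | 0.7972 | 28 |

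Example, first row: δ = 0.5 × √(64 × 64/128) = 2.828, t(0.975, 126) = 1.979, power 0.8015.

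No row gives 42. The two-sided t test returns 42 only for d between 0.886 and 0.909.

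**Step 2: which calculations do return 42?**

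- A three-group one-way ANOVA with f = 0.5: F(2, 39), noncentrality 0.25 × 42 = 10.5, power 0.8034. The next smaller balanced size, 39, gives 0.7688.
- A two-group MANOVA with f² = 0.25 and two outcomes: the same F(2, 39), power 0.8034.
- A one-sided two-sample t test with d = 0.8: 21 per group, power 0.8168 (20 per group gives 0.7994).

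None is a two-sided two-sample t test at 0.5. The documents do not show which calculation was run, so I infer no cause.

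**Step 3: what the available numbers deliver** (two-sided, alpha 0.05). The figure of 45 is 60 × 0.75, taken as 22 + 23.

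| Analysed | Detectable d, 80% power | Power at d = 0.5 | Power at d = 1.0 | 95% CI half-width (SD) |
|---|---|---|---|---|
| 42 (21 + 21) | 0.886 | 0.353 | 0.885 | 0.624 |
| 45 (22 + 23) | 0.855 | 0.374 | 0.906 | 0.601 |
| 60 (30 + 30) | 0.736 | 0.478 | 0.968 | 0.517 |

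The half-width is t(0.975, N − 2)·√(1/n1 + 1/n2). For 60 it is 2.002 × 0.258 = 0.517. Since 0.517 and 0.601 both exceed 0.5, an observed difference of exactly zero would still leave d = 0.5 inside the interval with 60 or 45 analysed.

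One-sided power at d = 0.5 would be 0.479, 0.502 and 0.606, still well short of 80%.

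**Step 4: sensitivity to uneven dropout among 45.** A 27 + 18 split gives a detectable d of 0.872 and power of 0.362 at d = 0.5. A 30 + 15 split gives 0.906 and 0.340. The picture does not change.

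**Side note on dropout.** 42/0.75 = 56, not 60, whereas 42/0.70 = 60. The stated 25% does not give 60, but the difference is towards more participants.

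**The case against.** The strongest counter-argument is that underpowering has not been shown. The metric is open. If 0.5 is f, 42 exceeds the 34 required and power is 89% to 97%. Moreover, the one ANOVA setting that literally uses 0.5 and returns 42 uses f. That stands: low power is established only under the d reading. What does not depend on the reading is that the stated inputs fail to give the stated number for the planned test.

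Second, section 2.6 names no test, so the link to the t test is the reader's. It is, however, the only outcome test the plan names, and it fits the two groups and the non-directional hypotheses. The correlation objective in section 1.2 does not rescue the figure: r = 0.5 needs about 29. Section 2.6 also cites a 2021 source that is absent from the reference list. It may explain the settings, but a reader cannot see that from the plan.

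Third, the correction changes neither the data nor the test, and after the trial the interval matters more than a planning sentence. This is true and is why the fix is cheap. It does not justify leaving in place the plan's only claim about what the trial can detect when that claim is wrong for the planned test.

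Fourth, the plan does not say that a non-significant post-treatment result will be read as equivalence, and the interval point is close at 60 (0.517 against 0.5). Both are fair. A single d also says nothing about clinical relevance, about the many outcomes listed in section 2.11, or precisely about a 0 to 5 strength grade.

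**Conclusion.** The concern holds. For a two-sided two-sample t test in two equal groups at alpha 0.05 and 80% power, the stated 0.5 requires 128 (as d) or 34 (as f), not 42. Independently of the metric, the detectable effect is d = 0.85 if 45 are analysed and 0.74 if all 60 are. If 0.5 was meant as d, power is 37% and 48% at those sizes; if it was meant as f, 91% and 97%, for a difference of one standard deviation.

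These figures assume the t-test model (roughly normal data with equal variances), unadjusted post-treatment values, a single comparison at 0.05, and near-even dropout for the 45. This must be corrected, because the sample-size statement is wrong as written and readers will rely on it.

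**What to change.** Keep 60 participants and the planned test.

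1. In section 2.6, replace the claim of 80% power at 0.5 with 42 by a statement that is true whatever metric was entered. For example: *With 60 randomised and 25% dropout, about 45 analysed give 80% power (two-sided alpha 0.05, two-sample t test) for a standardised mean difference of about d = 0.85, or 0.74 if all 60 are analysed. Power at d = 0.5 is about 37% and 48% respectively.* Adding the power at d = 1.0 (about 91% and 97%) would avoid any suggestion that the 0.5 was d.
2. Name the outcome to which this applies and, from the saved G*Power settings, the test and metric behind the 0.5. If the settings are lost, say so and do not assign a metric afterwards.
3. In section 2.12, report each between-group difference with its 95% confidence interval, and state that a non-significant result will not be read as no difference.

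Minor: state which dropout allowance gives 60 (42/0.75 = 56; 42/0.70 = 60). This does no harm to power.

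The cost is a wording correction in section 2.6 and a reporting sentence in section 2.12. The one drawback is a less favourable power statement.

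### Section 2.6 derives 60 from 42 participants and 25% dropout, but those figures give 56; the 4 extra are on the safe side, and the power shortfall comes from the base of 42

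*Combined protocol and SAP*

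**What the plan says.** Section 2.6 (Sample Size) of the combined protocol and SAP gives the inputs as "power 80% effective size 0.5, type I error = 0.05 and type II error = 0.2" and the result as "Therefore calculated sample size was 42". The allowance for loss follows: "Drop down rate of participants is assigned as 25 %. Therefore final sample size which obtained is 60". No inflation formula is shown, and no rounding is mentioned.

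Section 2.7 (Sampling method) says that "30 Participants will be randomly allocated to each group", and section 2.8 (Data collection) says the same: "Thirty participants will be allocated randomly to each group". So 60 is the total for both arms.

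Section 2.12 (Data analysis) names a two-sample t test for the comparison after the intervention. The hypotheses in section 2.5 are two-sided; for pain intensity the alternative is "There is a difference in pain intensity of participants between experimental and control group". Section 2.6 does not say whether 0.5 is Cohen's d or another effect size, whether the calculation was one- or two-sided, or whether 42 is a total or a number per group.

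**The concern.** The paragraph presents 60 as the consequence of 42 and 25%, and neither usual way of allowing for dropout gives it. This is the trial's only sample-size justification. A reader who checks it cannot see why 60 was chosen or how many completers the plan expects. The expected number of completers matters because the power of the planned test depends on it, and the plan gives power only as an input to the calculation, never for the number it expects to analyse.

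**Working it through.** **Inputs.** From section 2.6: base 42, dropout 25%, final size 60, effect size 0.5, alpha 0.05, power 80%. From sections 2.7 and 2.8: 30 per group. From sections 2.12 and 2.5: two-sample t test, two-sided alternative. I read 42 as a total, because the 60 derived from it is a total.

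**1. Trying to reproduce 60.**
- Standard inflation, N/(1 − loss): 42/0.75 = 56. Per arm, 21/0.75 = 28 exactly, so equal arms need no rounding.
- Shortcut, N × (1 + loss): 42 × 1.25 = 52.5, so 53, or 54 for equal arms.
- With 42 read as per group: 42/0.75 = 56 per group, 112 in total.

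None gives 60.

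**2. What would give 60.** 45/0.75 = 60, 48 × 1.25 = 60, or 42/0.70 = 60. The first two need a base other than 42, and the third needs 30% loss. None of these inputs is in the documents.

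**3. Direction and size.** 60 − 56 = 4 participants, or 2 per arm. At the stated loss, 60 × 0.75 = 45 completers (22 and 23 per arm), which is 3 more than 42.

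**4. Power for the numbers expected.** Noncentral t, two-sided alpha 0.05, d = 0.5, noncentrality d × √(n/2) with n per arm:

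| Completers | Power at d = 0.5 | d for 80% power |
|---|---|---|
| 42 (21 per arm) | 35% | 0.89 |
| 45 (22 and 23) | 37% | 0.85 |
| 60 (30 per arm) | 48% | 0.74 |

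One-sided, the three power figures would be 48%, 50% and 61%.

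**5. Source of the shortfall.** The same test at d = 0.5, alpha 0.05 and 80% power needs 64 per arm (128 in total) two-sided, or 51 per arm (102 in total) one-sided. Other routes to 42 were tried:
- A paired t test at 0.5 needs 34 two-sided or 27 one-sided.
- A one-way analysis of variance with f = 0.5 needs 34 in total for two groups and 42 for three.
- With 42 per group, a two-sample t test has 62% power two-sided and 73% one-sided.

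Of these, only the three-group calculation returns 42, and this trial has two groups.

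**The case against.** The strongest reply is that nothing goes wrong in practice. The gap is small, it errs towards more participants, and rounding 28 per arm up to a convenient 30 would explain it; sections 2.7 and 2.8 both use 30. Most of this stands. The plan needs 42 completers and at its own loss rate can expect 45. What does not stand is the rounding as an explanation, because section 2.6 never mentions it and attributes 60 to the dropout rate.

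A second reply is that the plan is not really ambiguous: it gives one loss rate, 25%, and 42 and 45 are the required and the expected number of completers. That is right. A reader might infer from 42/0.70 = 60 that the plan tolerates 30% loss, but that rate is only a back-calculation and appears nowhere in the documents.

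A third reply is that the low power has nothing to do with this step. That also stands. A reader might infer that the inflation step costs the trial its power, but at d = 0.5 the power is 35% with exactly 42 completers and only 48% if all 60 complete. The power belongs in this point only because the paragraph has to be rewritten anyway, and correcting the inflation alone would leave the 80% claim standing.

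**Conclusion.** The inflation step is wrong as written: 42 with 25% loss gives 56, not 60. Taken alone this is a minor error of 4 participants in the conservative direction. It might be taken to mean that the recruitment target is too low to deliver 42 completers; the plan's own figures show the opposite.

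The weightier problem in the same paragraph is the base of 42, which does not follow from the stated inputs for the planned test. The power figures rest on three assumptions: 0.5 is Cohen's d, the test is two-sided as section 2.5 implies, and losses are about equal between arms. A one-sided test would raise the power with 45 completers to about 50%, still well below 80%. The reading of 0.5 matters more. If it were f, a two-group comparison would need 34 in total, and 42 would be more than enough. Section 2.6 does not say which was meant, but Cohen's d is the usual effect size for the t test that section 2.12 names.

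**What to change.** Keep 60 (30 per group) and rewrite the end of section 2.6:

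- Replace the inflation sentence with, for example: *42/0.75 = 56, set at 60 (30 per group); at 25% loss about 45 complete.* Give the reason for going from 56 to 60.
- Do not change the dropout rate to 30% to make the arithmetic close, and do not lower the target to 56. At 25% loss, 56 would leave 42 completers and slightly less power.
- State the G*Power test family, the sidedness, the type of effect size, and whether 42 is a total. Then correct or justify 42.
- Restate the power for the expected completers. Under the assumptions above, this is about 37% at d = 0.5 with 45 completers (48% if all 60 complete), with 80% power at d of about 0.85.

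The cost is a few sentences in one section. Enrolment, allocation and analysis do not change, but the stated power becomes much less favourable once 42 is no longer taken as given. If the sponsor wants to keep 80% power at d = 0.5, that is a separate decision about the base: 128 completers, and 128/0.75 = 171 enrolled (172 for equal arms).

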3. EXPECTED OUTCOME

The main outcome of this research study find the effectiveness of Thoracic mobility exercise in comparison with manual release technique in treating upper back pain. Over all expected outcome of the research is thoracic mobility exercise will be more effective than manual release technique which includes myofascial release and Maitland's thoracic mobilization technique. Thoracic mobility exercises involve a series of movements and stretches aimed at improving the flexibility, range of motion, and strength of the thoracic spine and spinal extensors. These exercises can target specific muscle groups and promote better posture and spinal alignment. It is anticipated that thoracic mobility exercises will help patients by addressing the root causes of upper back pain. These exercises may improve posture, reduce muscle imbalances, and increase the overall mobility of the thoracic spine.

Myofascial release involves applying sustained pressure to specific trigger points or knots in the muscles and fascia of the upper back. Maitland's thoracic mobilization technique, on the other hand, is a hands-on manual therapy approach that focuses on joint mobilization and spinal manipulation. It provide immediate pain relief by targeting specific areas of tension or dysfunction in the upper back.

In this research, Pain intensity is measured using VAS Scale; Both intervention targeting pain relief; therefore it provides significant pain relief after the administration. In terms of Range of Motion, Strength and Disability, thoracic mobility exercise will provide more improvement compared to the manual therapy technique. Thoracic mobility exercise will provide long term benefit when compared to the manual therapy technique by eliminating root cause of upper back pain.

4. REFERENCES:

Akulwar-Tajane, I. *et al.* (2021) 'Effects of COVID-19 pandemic lock down on posture in physiotherapy students: A cross-sectional study', *Medical & Clinical Research*, 6(1), pp. 91–102.

Amro, A. *et al.* (2020) 'Musculoskeletal disorders and association with social media use among university students at the quarantine time of COVID-19 outbreak'.

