3.3 What are the treatments that you underwent so far?

.....

In the following scale, mark a number which best describes your pain. Number “0” indicates “no pain at all”, and number 10 indicates “the worst pain ever possible”. You

have to denote the number which best describes your pain in following instance and please denote the number respective to each activity in the following chart.

Aspect	VAS/ Pain scale number

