5.2.2 Post Test Questionnaire

[figure not shown]
Effectiveness of Thoracic mobility exercises versus manual release technique in minimizing mechanical upper back pain among undergraduates in Sri Lanka

Post Test Questionnaire

Code No:.....

1. Pain related questions:

In the following scale, mark a number which best describes your pain. Number “0” indicates “no pain at all”, and number 10 indicates “the worst pain ever possible”. You have to denote the number which best describes your pain in following instance and please denote the number respective to each activity in the following chart

Aspect	VAS/ Pain scale number
1.1Present Pain Intensity	
1.2Sitting	
1.3forward Bending	
1.4Standing	
1.5Walking	
1.6Sleeping	
1.7Transferring	
1.8Performing day to day activities	

2. Range of Motion (ROM)

Joint	Movement	ROM
Thoraco- Lumbar	Flexion	
	extension	

5. Muscle Strength

Muscle strength of Thoracic spine extension	MMT Scale (Oxford- Grading Scale)

6. Pain- Self- efficacy Questionnaire (PSEQ)

Please rate how confident you are that you can do the following things at present, despite the pain. To indicate your answer tap one of the options on the scale under each item, from "not at all confident" to "completely confident".

(Fill the appropriate field only)

	0 "not at all confident"	1	2	3	4	5	6 "completely confident"
I can enjoy things, despite the pain.							
I can do most of the household chores (e.g.							

tidying-up, washing dishes, etc.), despite the pain.						
I can socialise with my friends or family members as often as I used to do, despite the pain.						
I can cope with my pain in most situations.						
I can do some form of work, despite the pain. ('work' includes housework, paid and unpaid work).						
I can still do many of the things I enjoy doing, such as hobbies or leisure activity, despite pain.						
I can cope with my pain without medication.						
I can still accomplish most of my goals in life, despite the pain.						
I can live a normal lifestyle, despite the pain.						
I can gradually become more active, despite the pain.						

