5.3 Annex III: Treatment Protocol

Experimental Group:

Thoracic Mobility exercises

1. Cat and Camel exercise:

Subject has to position himself on their hands and knees on the floor. Head has to be in relaxed position and allowed to drop down (figure 5.3.1). First, Subject has to round his back toward the ceiling until he or she feel a nice stretch in his or her upper and middle back. When Perform this technique subject has to inhale (figure 5.3.2). Hold this stretch for 10 seconds. Then subject has to return to the starting position with flat back. While doing this subject has to exhale. Subject has to let his back sway by pressing his or stomach toward the floor (Figure 5.3.3). Hold this Position for 10 seconds. Repeat for 5 times.

Figure 5.3.1

Figure 5.3.2

Figure 5.3.3

2. Horizontal Chest Expansion:

Subject has to stand shoulder width apart. Bring the hands in front of the body to the shoulder level and palm of each hand to be touched each other (parallel to the floor)(figure 5.3.4). While breathing in or inhaling bring both hands apart from each other to the side and go beyond the side of the body (Figure 5.3.5). After that, This Position has to hold for 10 seconds. Then, while exhaling hands have to return back to the normal position. Exercise has to repeat for 5 times.

Figure 5.3.4

Figure 5.3.5

3. Cross arm chest expansion:

Subject has to stand shoulder width apart. Subject has to gently cross arms, so that finger tips point to the opposite shoulder. Then, Subject has to keep the lower body stable and turn the upper body from side to side allowing with head to follow the movement. Subject has to keep the movement controlled and smooth (figure 5.3.6). Repeat 5 times.

Figure 5.3.6

Subjects has to perform these exercise two times a day. Exercise has to be performed with 5 minutes break for up to two weeks. Participants to be examined 3 times in a week whether they performed correctly.

Control Group:

Myofascial release:

Participants will be properly placed in prone lying position and adequate Therapist will palpate the muscle (spinal extensors) and trigger points will be identified. Constant pressure will be applied for 90 seconds to release the painful points as illustrated in Figure 5.3.7

Figure 5.3.7

Thoracic Spine Mobilization (Maitland technique):

Postero-anterior central vertebral pressure:

Starting position:

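### The two-week form has no item for new symptoms, reasons for stopping treatment or other treatment used, so harms beyond worse back pain, and co-treatment, could not be described by arm

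*Combined protocol and SAP*

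**What the plan says.** Section 2.9 describes a post-test questionnaire of four sections, covering "mainly pain intensity after two weeks, muscle strength after two weeks, Range of motion after two weeks and pain-self-efficacy Questionnaire (PSEQ"). Section 2.11 defines the two-week data by subtraction from baseline: "After two weeks same outcome measures will be obtained other than demographic characteristics and pain duration". Treatment is not on the baseline outcome list, so this sentence does not carry it forward.

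The form in Annex 5.2.2 is printed item by item. Its pain block ends at "1.8Performing day to day activities". After that come flexion and extension range, one Oxford grade and the ten PSEQ items. Its only mention of medication is a PSEQ confidence rating, "I can cope with my pain without medication".

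The one question about treatment is item 3.3 of the pre-test form (Annex 5.2.1): "What are the treatments that you underwent so far". It is not repeated at two weeks.

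On eligibility, section 2.8 says "those who are having any contraindications, recent surgeries, fractures, accidents will be excluded". Neither this text nor the treatment protocol in Annex III mentions other treatment during the trial. Section 2.12 plans two-sample t tests, with no summary of harms or co-treatment.

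**The concern.** The trial compares exercise that participants perform themselves with manual treatment. Of the manual treatment, Annex III says "Constant pressure will be applied for 90 seconds to release the painful points", and spinal mobilisation is added. Anyone choosing between the two would want to know how each was tolerated. Soreness that settled before the two-week visit, a symptom elsewhere in the body, or a decision to stop because of discomfort would leave no trace on the form.

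Co-treatment matters for interpretation. Section 3 expects to credit the exercises themselves: "It is anticipated that thoracic mobility exercises will help patients by addressing the root causes of upper back pain". If one arm took more painkillers or sought more outside care, part of a pain difference could come from that. With no record of use, even a large imbalance would go unseen.

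**Working it through.** **Step 1. Is the information anywhere in the two-week data?** The plan states no figure on this point, so the first check sets the sources side by side.

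| Information | Nearest item | What it gives |
|---|---|---|
| Worse back pain | Eight pain ratings, asked identically at baseline (3.4 to 3.11) and two weeks (1.1 to 1.8) | Change by arm can be tabulated |
| Number lost | Post-test forms not returned | Count by arm, without reasons |
| New or passing symptom | None | Nothing |
| Reason for stopping treatment | None | Nothing |
| Medicines or other treatment in the two weeks | Item 3.3; PSEQ item 7 | Treatment before entry; confidence, not use |

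Annex III has exercise participants seen three times a week, but only to check performance. No contact frequency is stated for the manual arm. Sections 2.9 and 2.11 and Annex 5.2.2 agree with one another, so the last three rows are gaps in the plan.

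**Step 2. How many would answer?** Section 2.8 allocates 30 per arm and section 2.6 allows 25% dropout. Completers: 60 × 0.75 = 45, or about 22 per arm. An arm with 22 completers has 30 − 22 = 8 others.

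**Step 3. What could a symptom item show?**

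- No cases, one-sided 95% upper limit, 1 − 0.05^(1/n): 1 − 0.05^(1/22) = 12.7%; 1 − 0.05^(1/30) = 9.5%.
- Chance of at least one case in an arm, 1 − (1 − r)^n, for an assumed true rate r. At 5%: 1 − 0.95^22 = 68% and 1 − 0.95^30 = 79%. At 10%: 1 − 0.90^22 = 90% and 1 − 0.90^30 = 96%.
- If none of 22 completers reports a symptom and the other 8 are not asked, the proportion among the 30 randomised lies anywhere from 0/30 = 0 to 8/30 = 27%. This assumes that those who withdraw do not fill in the form, which the protocol does not say.

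**Step 4. What could a co-treatment item show?** The documents give no rate of use, so p below is assumed equal in both arms. The half-width of the 95% interval for the difference is 1.96 × √(2p(1 − p)/n).

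| Assumed p | n = 22 per arm | n = 30 per arm |
|---|---|---|
| 10% | ±18 points | ±15 points |
| 20% | ±24 points | ±20 points |
| 30% | ±27 points | ±23 points |

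For example, p = 20% and n = 22 give 1.96 × √(0.32/22) = 0.236. At p = 10% and n = 22 only about 2 users per arm are expected (0.10 × 22 = 2.2). The formula is rough there, and that cell is an order of magnitude only.

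**The case against.** The strongest reply is that much of what matters is already collected. Worse back pain is an obvious harm of pressing on painful points or exercising a painful back, and the eight ratings capture it at both time points. Losses can be counted. Section 2.8 excludes people with contraindications, and Annex III adapts the mobilisation grade to pain. None of the stated objectives or hypotheses concerns harms. All of this stands, and it limits the point to other symptoms, reasons for stopping, and co-treatment. The safeguards reduce risk but record nothing.

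A second reply is that co-treatment counts this imprecise could never show that use was similar in the two arms, nor separate its effect from that of the therapy. That also stands. The case for the item is that a large imbalance would become visible.

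Three stronger readings are tempting and not supported:

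- **That tolerability cannot be described at all.** Pain change and losses by arm remain available.
- **That unrecorded co-treatment invalidates the pain comparison.** The arms are randomised. The t test compares assignment to each therapy, including whatever other treatment follows. What is limited is attributing a difference to the therapy itself.
- **That the trial has no rule on other treatment and no follow-up of withdrawals.** None appears in the text reviewed, but consent and some other pages were not part of that text, and its appendices begin at Annex II. Instructions to participants could be there. They would not add an item to the printed post-test form.

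**Conclusion.** The point holds in limited form. If the plan is followed exactly, nobody could report by arm, from the stored data, new or passing symptoms, reasons for stopping, or treatment used during the two weeks. Asking participants afterwards is possible but relies on longer recall. The main comparison is unaffected, and no sample size changes.

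The gain from closing the gap is modest. The data would probably reveal a reaction affecting one participant in ten, and could miss one affecting one in twenty. They would expose only a large imbalance in co-treatment. The ranges rest on 22 to 30 respondents per arm and on assumed rates of harm and use. That the items are missing rests on sections 2.9 and 2.11 and the printed form alone.

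**What to change.** Add two self-completed items for both arms, on a sheet carrying the participant's code:

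1. Any new or worse symptom since starting, and whether and why the allocated treatment was stopped.
2. Item 3.3 repeated for the two-week period, naming medicines and other treatment for this pain.

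Have the sheet returned so that the blinded assessor does not see it. Report both items as descriptive counts by arm, with the number answering, beside tabulations of worsened pain and losses. State in the plan that the counts can show only common harms or a large imbalance in co-treatment. Keep users of other treatment in the analysis, because use is decided after randomisation. Do not substitute therapists' notes: a contact frequency is stated for one arm only, so the arm seen more often could yield more events.

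Asking the same items of people who withdraw is optional. It is best done at the moment of withdrawal, and only where consent allows. Later contact would mean re-linking personal details that section 2.9 keeps separate, and approaching people who have used their right to leave.

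The cost is a few minutes per participant, and someone other than the assessor to receive the sheets. The downsides are imperfect two-week recall, a risk of unblinding if the assessor sees the sheet, and incomplete counts if people who withdraw are not asked.
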